All goals of the pilot project were successfully achieved, via multiple rounds of interviews and focus group discussions conducted with high-risk smokers recruited by the HealthPartners Institute. Multiple versions of the Report were created and tested in the qualitative research using historical screening images for the Image section and fictional risk metrics for the Comparative section. Information gathered from each round informed the design of the subsequent round to improve participant comprehension and increase emotional impact of the Report.

The final round of focus groups, a questionnaire incorporating the Contemplation Ladder and Smoking Hazard scales, as well as a Self-efficacy Scale was used to assess the overall psychological impact of the Report design. Responses supported the hypothesis that a personalized version of the Report would likely have a positive impact on a participants' motivation to make a quit attempt, by increasing their hazard perception, and strengthening their belief in their ability to quit. Final focus group feedback indicated that participants were engaged by the Report and were very optimistic about its potential impact on smokers. Participants felt confident the Report would encourage smokers to make a quit attempt, especially when included as part of a smoking cessation discussion with a medical professional.

In conclusion, all milestones were successfully completed for the Phase I pilot. The Report design was dramatically improved for comprehension, personalization, and motivational content and design, and shows strong promise to increase quit attempts by motivating patients to access smoking cessation resources including a quitline, other formal cessation programs, and/or cessation medications.

Randomized Control Trial Study Design

The RCT will enroll approximately 400 self-selecting participants (200 at HealthPartners, and 200 at The University of Michigan) using a 2 by 2 factorial design from lung cancer screening programs at HealthPartners and the University of Michigan Heath Services.

INCLUSION CRITERIA:

Specific Inclusion Criteria (based on NLST guidelines) include the following:

- Age 55-74
- Smoking history of \geq 30-pack years
- Currently actively smoking cigarettes
- Ability to read, write and communicate in English
- Screening CT scheduled at the HP Specialty Center ([name])
- Available by telephone for counseling and/or follow-up communications

EXCLUSION CRITERIA

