- Clinically significant health problems that make projected lifespan \leq 2-years
- LungRads Category 3 or 4 resulted out on screening CT

Recruitment and Consent - Randomized Controlled Trial participants will be recruited through the University of Michigan (200 participants) Health System and the HealthPartners Institute (200 participants).

- At HealthPartners, patients scheduled at HealthPartners Specialty Center will be given an informational flyer and consent form with return envelope during check-in for their Screening CT.
- Patients interested in participating in the study will be asked to contact the study coordinator by telephone within 72-hours (3-days) of their CT scan. During that call the coordinator will review the study requirements, read the consent form to the participant and attest to the patient's willingness to participate in the study. Participant will be asked to mail the last (signature) page of the consent to the coordinator in the envelope provided for back up hard copy.
- Consent forms will specifically request permission to share actual CT images with IMBIO in order to print a Patient Report based on the patient's own CT images. Specific permission will also be sought to share the Patient Report CT screening results with Mayo TTS and the Quitline representative.
- Following the screen, a radiologist will analyze the CT scan image and send the results to the patient's PCP. If the scan is read as a category 1 or 2 in the Lung CT Screening Reporting and Data System (Lung-RADS) [49], patients who have consented to study participation will be randomized to one of four treatment arms. If the scan is read as a category 3, 4A, 4B, or 4X in Lung-RADS the patient will be contacted by their primary care physician's office and told to schedule a follow up appointment. They will be sent a letter informing them they are not eligible for participation in the study after ordering physician has notified them of results and follow-up plans.

Randomization

Upon attestation of consent, eligible participants will be randomly assigned to one of four conditions using a central RedCap database:

1. Usual Care (w/ MN Quitline phone number);
2. Usual Care + Report (w/ IMBIO Quitline number);
3. Usual Care + Counseling; Or
4. Usual Care + Report (w/ IMBIO Quitline number) + Counseling incorporating results of report.

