Data management - Data will be stored in a secured, centrally located REDCap database. Investigators will oversee the REDCap database setup, data management, audit and edit plans to ensure data accuracy and completeness, and creation of the study's codebook with precise definitions and coding of all variables. A double-checking mechanism will be set up to ensure data completeness and accuracy. Strategies are set up for handling missing data, which are described below.

VI. Data Analysis, Sample Size and Statistics - [name], a biostatistician with the University of Minnesota School of Public Health, will analyze data from the RCT. Similar to standard methods for factorial designs in other therapeutic areas, analyses to address the primary aims will be a test of the main effect of the randomized interventions (i.e., report type and counseling type). All analyses will be by intention-to-treat, and include all participants randomized, regardless of whether they are lost to follow-up. The primary outcome measures will be a dichotomous comparison of 24-hour quit attempts (yes/no) at the time of the three-week follow-up, three-month follow-up, and six-month follow up and subject-reported readiness to quit based on the contemplation ladder among those who have not quit smoking. Secondary outcomes include cotinine-verified abstinence at three and six-months and use of smoking cessation services (dichotomous outcome) at 3 weeks, 3 and 6 months. Initially assessment will focus on the main effect of Report condition (Report vs. Usual Care) averaging or "pooling over" the Counseling condition on the continuous (readiness to quit) and dichotomous outcomes (24-hour quit attempt, abstinence, use of smoking cessation services) using a two sample t-test of the difference in the mean response and two-sided Wald-type test [60] of the difference in proportions, respectively, with a 0.05 significance level. Exact tests (e.g., Barnard's exact test) may be used if the number of successes (e.g., quit attempts, abstinence) is

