Power for these primary hypotheses are shown in Table 2 assuming 400 total subjects under different assumptions concerning the average response within each of the randomized groups. A difference of 20% and 12.5% is considered between the Report and Usual Care conditions to be of interest for the percentage of subjects with at least one 24-hour quit attempt and accessing cessation programs/medication within 6 months. Similarly, an average difference of 1.5 on the contemplation ladder is considered meaningful. Table 2 indicates there is sufficient power to detect these differences and even reasonable power across many scenarios to detect smaller effects for the main effect of the Report. Additionally, Table 2 demonstrates that there is adequate power to detect a significant effect of the Report within each level of the counseling condition at the 0.1 significance level.

Concerning 6-month abstinence, differences were considered between the Report and Usual Care between 5-10% to be meaningful. As a Phase II study, it is not powered to detect a significant main effect for the Report for the 6-month abstinence outcome. However, Table 3 demonstrates that across a range of plausible scenarios there is sufficient power for a composite test of whether or not the probability of abstinence at 6 months is the same across all 4 arms and whether or not the Report + Counseling is different than Usual Care.

As part of the analysis, it is expected that Report Only compared to Usual Care will significantly increase readiness to quit, quit attempts, and accessing of programs/medications. It is also expected that the Report + Counseling will produce significantly higher 7-day point prevalence abstinence at 6 months than Usual Care with the other two conditions intermediate. In particular, it is expected that the combination of counseling and the Report will be more effective in increasing readiness to quit, quit attempts, use of formal programs and/or medications and abstinence than the other three conditions. Additionally, it is expected that 5% in the

Outcome	Percentage or Mean				Power to Detect a Significant Effect of Report		
	Usual Care	Report Only	Usual Care + Counseling Only	Report + Counseling	Main Effect (averaged over counseling conditions)	Within No Counseling Condition	Within Counseling Condition
24 hour quit attempts	20%	40%	40%	60%	98.7%	93.5%	89.3%
	20%	35%	35%	50%	89.2%	77.7%	69.4%
Accessing Services and/or Medication	5%	17.5%	17.5%	30%	92.4%	88.9%	67.6%

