	5%	15%	15%	25%	81.2%	77.2%	55.1%
Readiness to Quit	6.0	7.5	7.5	9.0	99.9%	97.8%	97.8%
	6.0	7.0	7.0	8.0	93.2%	78.6%	78.6%

the Imbio report and usual CT scan report. Power calculations assume total N=400 and the use of a two-sided test with a 0.05 significance level for the main effect and 0.10 significance level for the effects within each counseling condition level. The power calculation for readiness to quit assume a standard deviation of 2.9 on the contemplation ladder.

Usual Care condition will make a quit attempt (24-hour quit) versus 15% in the Report condition at the time of the 3-week follow-up. The Report will yield significantly greater percentage of subjects reporting a quit attempt at 3 and 6 months.

VII. Title 21 FDA Device Trial Regulations

The IMBIO **Patient Smoking Cessation Report** is currently preparing to undergo the proposed RCT in preparation for eventual FDA approval as a medical device. This trial will be run under the non-significant risk (NSR) section of Title 21 FCR 812.2(b) and will follow the abbreviated trial requirements contained therein. CFR 812.2(b) is uploaded with this application. Also uploaded is Title 21 CFR 56.111, which gives the IRB criteria for approval of NSR clinical device research under the abbreviated requirements associated with FCR 812.2(b).

The IMBIO Patient Smoking Cessation Report, as an NSR device, is not required to seek IDE approval through the FDA prior to starting the clinical trial proposed in this application. IRB agreement that this device qualifies as an NSR device will suffice in lieu of a formal IDE application, as long as said determination of NSR status is transcribed into formal IRB minutes.

This clinical trial will be monitored by the sponsor of the trial, IMBIO, LLC, in accordance with the monitoring requirements found in Title 21 CFR 812.46.

Following the conclusion of the clinical trial proposed in this application, the sponsor will approach the FDA for approval or clearance as a medical device.

VIII. Study Timeline

Phase II Work Plan	2016			2017												2018												2019															
	Oct	Nov	Dec	Jan	Feb	Mar	Apr	May	June	July	Aug	Sept	Oct.	Nov.	Dec.	Jan	Feb	Mar	Apr	May	June	July	Aug	Sept	Oct.	Nov.	Dec.	Jan	Feb	Mar	Apr	May	June	July	Aug.								
Recruit RCT participants																																											
SUBMIT mayo IRB application (with questionnaire developed in SA2)																																											

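### Table 2 computes power for every outcome at the full 400 enrolled, with no allowance for loss and although readiness is analysed only among non-quitters, so the printed powers are a best case

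*Combined protocol and SAP*

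**What the plan says.** - **Sample used for power.** The Table 2 note gives one sample size for all three outcomes: "Power calculations assume total N=400 and the use of a two-sided test with a 0.05 significance level for the main effect". Comparisons within a counseling level use a "0.10 significance level for the effects within each counseling condition level".
- **Enrolment.** The Randomized Control Trial Study Design section plans the same number: "The RCT will enroll approximately 400 self-selecting participants (200 at HealthPartners, and 200 at The University of Michigan").
- **Readiness analysis set.** Section VI, Data Analysis, defines this primary outcome as "subject-reported readiness to quit based on the contemplation ladder among those who have not quit smoking".
- **Loss to follow-up.** The same paragraph says all analyses are by intention-to-treat and "include all participants randomized, regardless of whether they are lost to follow-up". Section V announces strategies for missing data, but no rule follows in the text. No expected loss rate or quit rate is stated.
- **What is concluded.** Section VI, Sample Size, names 20 points (quit attempts), 12.5 points (programs or medication, called services below) and 1.5 ladder points as the differences that matter. On the Report main effect it claims "sufficient power to detect these differences and even reasonable power across many scenarios to detect smaller effects".

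**The concern.** The number enrolled and the number used for power are the same, so Table 2 is exact only if all 400 participants contribute full information to every outcome.

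For readiness this cannot happen in a trial where anyone quits, because the analysis definition removes quitters. That mismatch needs no assumption about follow-up.

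For the yes/no outcomes, keeping everyone randomized in the analysis does not supply outcomes that were never observed. If unobserved participants are left out, N falls. If they are counted as having no event, N stays at 400 but equal loss across arms shrinks the difference in proportion.

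The claim about smaller effects is what is at stake. A reader who takes the printed 93.2%, 89.2% and 81.2% as expected power would place too much weight on a non-significant result at those differences.

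**Working it through.** **Inputs from the documents.** Total N = 400; two-sided alpha 0.05 for the main effect; SD 2.9 on the ladder; arm rates as printed in Table 2. Equal allocation (100 per arm, 200 versus 200 for the Report main effect) is not stated but reproduces the table.

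**Assumptions.** Loss of 10% or 20% and quit shares of 10% or 20%, equal across arms. Neither rate is in the documents.

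**1. Readiness.** Power ≈ Φ(δ / (2.9 × √(4/N)) − 1.96), with N = 400 × (1 − loss) × (1 − quit share).

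- Reproduction at N = 400, δ = 1.0: 1.0 / (2.9 × 0.1) = 3.448; 3.448 − 1.96 = 1.488; Φ = 93.2%, as printed.
- N = 360: 1.0 / (2.9 × 0.1054) = 3.271; Φ(1.311) = 90.5%.
- N = 288: 1.0 / (2.9 × 0.1179) = 2.926; Φ(0.966) = 83.3%.

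| Quitters | Loss | N | Power, 1.5 points | Power, 1.0 point |
|---|---|---|---|---|
| 0% | 0% | 400 | 99.9% | 93.2% |
| 10% | 0% | 360 | 99.8% | 90.5% |
| 10% | 10% | 324 | 99.6% | 87.4% |
| 10% | 20% | 288 | 99.2% | 83.3% |
| 20% | 20% | 256 | 98.5% | 78.8% |

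At 1.0 point, 90% power needs N = 354 and 80% needs N = 266. Combined shrinkage above 46/400 = 11.5% takes power below 90%; above 134/400 = 33.5% takes it below 80%.

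**2. Yes/no outcomes.** The plan does not print its power formula, so two versions were used:

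- (a) Two-sample test on rates averaged over counseling: Φ((d − 1.96√(2p̄(1−p̄)/n)) / √(p₁(1−p₁)/n + p₂(1−p₂)/n)), with n = 200.
- (b) Four-arm Wald contrast: Φ(d/SE − 1.96), with SE = ½√(Σp(1−p)/n) and n = 100 per arm.

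Reproduction for the 5/15/15/25% services row:

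- (a) 0.10 versus 0.20: (0.10 − 0.0700)/0.03536 = 0.849, giving 80.2%.
- (b) Σp(1−p) = 0.49, SE = ½√0.0049 = 0.035, 0.10/0.035 = 2.857, giving 81.5%.

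The printed value is 81.2%. Across the four rows the printed powers lie between (a) and (b), or within 0.1 point of that range.

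Loss enters in two ways. Complete cases (CC) multiply n by (1 − loss). Missing counted as no event (MNE) keeps n and multiplies every rate by (1 − loss). Example for the same row at 10% loss, formula (b):

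- CC: SE = ½√(0.49/90) = 0.0369; 0.10/0.0369 = 2.711; power 77.4%.
- MNE: rates 4.5/13.5/13.5/22.5%; Σp(1−p) = 0.4509; SE = 0.0336; 0.09/0.0336 = 2.681; power 76.4%.

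Main-effect power in %, formula (a) to formula (b):

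| Row (difference) | Printed | No loss | 10% CC | 10% MNE | 20% CC | 20% MNE |
|---|---|---|---|---|---|---|
| Quit attempt, 20 points | 98.7 | 98.5-98.9 | 97.5-98.1 | 96.6-97.3 | 95.8-96.8 | 93.2-94.2 |
| Quit attempt, 15 points | 89.2 | 88.5-89.7 | 85.0-86.4 | 83.1-84.4 | 80.6-82.3 | 76.4-77.7 |
| Services, 12.5 points | 92.4 | 91.1-92.3 | 88.0-89.4 | 87.3-88.6 | 84.0-85.7 | 82.4-83.7 |
| Services, 10 points | 81.2 | 80.2-81.5 | 75.9-77.4 | 75.2-76.4 | 70.9-72.4 | 69.3-70.5 |

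**The case against.** **The table is not miscalculated.** It reproduces at N = 400, and that assumption is stated openly. This stands: the fault lies in the assumption, not the arithmetic.

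**The plan does not forecast loss.** A reader might infer that the plan expects dropout and that the design therefore cannot deliver the yes/no rows. The sentence on participants lost to follow-up is an analysis rule and carries no rate. Payments of \$20, \$20 and \$70 for the three calls may also limit loss. This stands: the shortfall on those rows is conditional, and only the readiness mismatch follows from the text alone.

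**Missing as no event is a worst case.** The powered outcomes are at least one event within 6 months, asked about at three calls. Someone who reports an event at an early call and is then lost is already a yes. Multiplying rates by (1 − loss) assumes that lost participants report nothing at any call. This stands, and those columns are a lower bound.

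**Readiness is not tied to 6 months.** At 3 weeks the plan expects 24-hour quit attempts in 5% under Usual Care and 15% with the Report. Dropping every one of them would leave 190 versus 170, or 360 in total, and about 90% power at 1.0 point. This stands: adding 20% loss to the quitters describes a late visit.

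**The main targets survive.** They do, so the documents do not support a reading that the trial is underpowered for its stated aims.

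None of this removes the central point. The readiness power belongs to a population that the readiness analysis will not have, and no row allows for any loss.

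**Conclusion.** The concern holds as a statement about best-case figures. Table 2 overstates power for readiness by the plan's own definition of that outcome, and for the yes/no outcomes as soon as any outcome information is lost. The sizes rest on assumed rates, equal across arms.

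- **Differences of interest:** little changes. The 20-point and 12.5-point effects keep at least about 93% and 82% at 20% loss under either handling of missing data. The 1.5-point effect keeps 98.5% with 20% loss and 20% quitters. The sufficiency statement for these three can stay.
- **Smaller effects:** the change is material. At 10% to 20% loss the 15-point quit-attempt row moves to about 76-86% and the 10-point services row to about 69-77%, the latter below 80% even at 10% loss. Readiness at 1.0 point moves to about 90% with 10% quitters and to about 83% with 20% loss added.

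A reader might also blame attrition for the low powers within the counseling condition, such as 69.4% and 55.1%. Those are printed values at N = 400. Describing them as adequate is a separate wording problem.

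Excluding quitters also conditions on a post-randomization outcome and sits badly with including everyone randomized. That is a question of bias, separate from this point about power.

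**What to change.** 1. State the expected loss rate and the expected share of quitters at each time point, with their basis.
2. Supply the missing-data rule that section V announces, since without it the recalculation has no defined basis.
3. Restate Table 2 with readiness at the projected number of non-quitters, and all outcomes under explicit loss (for example 10% and 20%). Show complete cases and missing as no event, labelling the latter a worst case.
4. Keep the sufficiency statement for the 20-point, 12.5-point and 1.5-point main effects. Qualify the claim about smaller effects, chiefly for the 10-point services row.
5. Separately, reword the description of within-counseling power so that it matches the printed values.

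The cost is one recalculated table, a few sentences and less favourable stated figures. Enrolment need not change.
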